Comparative Biosciences, Inc. offers GLP and non-GLP preclinical toxicology, efficacy, pharmacology, pharmacokinetics-pharmacodynamics, histopathology, and safety studies on all laboratory species. They are a fully-staffed, state-of-the-art, AAALAC-accredited purpose-built facility with both an in house histopathology laboratory and a full time quality assurance unit. They are registered with the FDA, USDA, and OLAW. Histopathology was read by certified veterinary pathologist.

None of the eyes manifested signs of clinical toxicity immediately following treatment. Histopathologic toxicity at the limbal zone was minimal and consisted of small microhemorrhage, with scattered lymphocytes and monocytes and some local edema seen in a few eyes. The majority of these findings were located in myocytes. However, no ocular muscles were treated in any animal during this study. The pathologic findings of focal hemorrhage, inflammation, and myocyte damage relate to artifact/crush injuries to the muscles/ocular surface that occurred using 0.5 forceps to position the eyes of the anesthetized rabbits in a way that permitted exposure of the treatment sites (Fig 1). **In all eyes, the anterior segment (cornea, iris, ciliary process, lens and sclera were within normal limits, as was the retina and optic nerve. Of note, none of the eyes treated with -40°C for 10 seconds had any histopathologic findings. The coldest temperature planned for the proposed study is -10°C (23°F) for 20 seconds.**

Figure 1 | Site of cryotherapy treatment, preclinical safety study

Risks of the Proposed Study:

The primary risks patients will be exposed to relate to those that occur with IVT (SCH, conjunctival hyperemia and injection, and corneal keratopathy). The risks of the CA device include mild ocular discomfort secondary to the cold temperature.

All patients will receive topical anesthetic drops (proparacaine) prior to focal anesthesia (either CA or SOC). These drops will help reduce the occurrence of pre-injection discomfort. The topical anesthetic drop will provide baseline anesthesia if there is minimal anesthetic effect achieved by cryoanesthesia. Topical proparacaine use as stand-alone anesthesia prior to intravitreal injections is one of the common methods of providing anesthesia and is considered within the standard of care for intravitreal injections (Blaha et al., 2011, Davis 2012).

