treatment will be marked. Next, one drop of proparacaine will be applied into the eye to receive at least 5 minutes before any additional steps. Once the patient is ready, another drop of proparacaine will be applied and the physician or his assistant will then swab the lids with betadine. The patient will then have lidocaine gel placed on the eye and left in place for a minimum of 3 minutes prior to IVT. The 3-minute waiting period is needed to allow the lidocaine gel to diffuse through the sclera. Following completion of numbing, the eyelids will be swabbed with betadine and the physician will place the lid speculum. The physician will use a caliper to measure 3 or 4 mm from the limbus of the eye, place a drop of betadine over this spot, wait 20 seconds and then administer the injection.

2.3.2.1 Allocation to Treatment:

Patients will be randomly assigned to 1 of the 4 CA treatment groups and the SOC arm. Patients will be randomized to have their first eye receive either CA or SOC.

2.3.2.2 Treatment Adherence/Study Compliance:

If a patient is does not require, or refuses, an injection in either eye, they will be removed from the study. Because IVT prevents blindness, the refusal of IVT is extremely rare. In addition, it is extremely rare for patient who have been determined to need IVT to have improvement in vision prior to IVT.

If patients withdraw from the study, we will plan to recruit additional patients to replace them.

2.3.3 **Follow-up Procedures:**

2.3.3.1 Procedures to Assess Efficacy:

Patients will record their subjective pain (pre-injection preparation pain, injection pain, and 24 hr post injection pain) using a visual analog scale (1 to 10, with 10 being severe pain and 1 being no pain). The study coordinator will call the patients within 4 hours after their injection to review their 4-hr post procedure pain scores with them. Patients will be asked to return in 24 hours for anterior segment examination and 24-hr post injection pain assessment. Patients treated on Friday will be asked to return on Saturday for their 24-hr post injection assessment.

2.3.3.2 Procedures to Assess Safety:

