Physicians will record the following common ocular side effects following IVT: SCH, conjunctival hyperemia, and conjunctival injection. These will be assessed via a slit lamp examination performed within 30 minutes and 24 hours of the administration of the intravitreal injection. Patients will undergo an anterior segment ocular examination 1 day following their intravitreal injection, and the physician will again record the presence of SCH, conjunctival hyperemia, conjunctival injection, and corneal keratopathy. In addition, each eye will be assessed for other signs of anterior segment toxicity, including AC reaction or hypotony. Patients will be assessed by a phone call 1 week after injection in each eye for any adverse events.

Physicians will score ocular side effects of CA and SOC. We will conduct interim analysis every 12 weeks or following every 10th patient treated, whichever happens first, and will suspend the study if there appears to be significantly more ocular side effects following CA. For the reasons laid out

above (in the device description), we believe this device is minimal risk and has a very low probability of causing ocular side effects.

2.4 Study Outcome Evaluations:

2.4.1 Study Endpoints.

Primary Endpoint:

1. Injection pain - Pain rating on a visual analogue scale (1 to 10)

Exploratory Endpoints:

1. Injection preparation pain - Pain rating on a visual analogue scale, 1 to 10.
2. 4-hr post injection pain - Pain rating on a visual analogue scale, 1 to 10.
3. 24-hr post injection pain - Pain rating on a visual analogue scale, 1 to 10.
4. Physician recorded time from initiation of treatment to completion of the intravitreal injection.
5. Physician scored patient response to pain (1: no pain/movement; 2: mild pain/movement 3: marked pain/movement with the injection)
6. Physician scored ocular side effects within 30 minutes of administration of the intravitreal injection and 1 day following the injection (SCH, conjunctival hyperemia, conjunctival injection, and corneal keratopathy): 1: No ocular side effects; 2: mild ocular side effects (trace to 1+ SCH, conjunctival hyperemia, conjunctival injection, or corneal keratopathy; 3: Marked ocular side effects (SCH involving at least 25% of the ocular surface, 2-4+ conjunctival hyperemia or conjunctival injection, or 2-4+ corneal keratopathy). In addition, each eye will be assessed for other signs of anterior segment toxicity, including AC reaction or hypotony.

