In accordance with applicable policies of the University of Michigan Institutional Review Board (IRBMED), the investigator-sponsor will report, to the IRB, any observed or volunteered adverse effect that is determined to meet all of the following criteria: 1) *associated with the investigational device or, if applicable, other study treatment or diagnostic product(s)*; 2) *a serious adverse effect*; and 3) *an unexpected adverse effect*. Adverse event reports will be submitted to the IRB in accordance with the respective IRB procedures.

Applicable adverse effects will be reported to the IRB as soon as possible and, in no event, later than 10 calendar days following the investigator-sponsor's receipt of the respective information. Adverse effects which are 1) *associated with the investigational drug or, if applicable, other study treatment or diagnostic product(s)*; 2) *fatal or life-threatening*; and 3) *unexpected* will be reported to the IRB within 24 hours of the investigator-sponsor's receipt of the respective information.

Follow-up information to reported adverse effects will be submitted to the IRB as soon as the relevant information is available. If the results of the sponsor-investigator's follow-up investigation show that an adverse effect that was initially determined to not require reporting to the IRB does, in fact, meet the requirements for reporting; the investigator-sponsor will report the adverse effect to the IRB as soon as possible, but in no event later than 10 calendar days, after the determination was made.

3.1 Withdrawal of Subjects Due to Adverse Effects:

Patients will only have a single exposure to the device (10 to 20 seconds in length). Should a patient not tolerate the discomfort of the cold tip for the entire duration and be unable to receive full CA, that patient would be removed from the study.

If a patient withdraws from the study, the patient data will be destroyed. Another patient will be recruited to take their place, provided that the additional patient can be recruited and treated within the allotted study time frame.

3.2 Monitoring Plan:

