This monitoring plan will be followed in monitoring the University of Michigan as a single site approved for performance of a Nonsignificant Risk Device protocol under FDA guidance for Significant and Nonsignificant Riske devices, entitled, Cryoanesthesia. As the scope of this study is utilizing a Nonsignificant risk device involving 40 adults, this monitoring plan will be performed by the Sponsor-Investigator (S-I). The monitoring frequency shall be as follows: after 20 participants have been enrolled and again after all 40 patients have been enrolled.

Purpose:

The purpose of the monitoring plan is to facilitate compliance with good clinical practices, FDA guidelines and regulations which require monitors to verify the following:

- The rights and well-being of participants are protected
- Reported data are accurate, complete, and verifiable from source documents
- Trial conducted in compliance with currently approved protocol and other applicable regulatory requirements

This document identifies key monitoring activities and specifies the date to be reviewed over the course of a clinical trial.

Site initiation and Qualification:

Prior to study initiation, the S-I will review the following information:

- IRB approved version of the approved protocol for the study
- IRB approved Informed Consent Forms and processes
- AE and SAE definitions and reporting procedure, including plans for S-I review of all adverse events. It is recommended that the S-I contact the Michigan Institute for Clinical and Health Research IND/IDE Assistance Program (MIAP) for assistance with any reporting requirements to the FDA.
- CRF completion and maintenance process
- Creation and organization of the Investigator Study Binder

Device accountability (e.g. access to storage, storage location, and dispensing of the device) will be maintained in study records. If not, the study records, state where the investigational product accountability records will be maintained.

Interim Monitoring:

At the two study team meetings (after enrollment of 20 subjects and again after enrollment has been completed), the S-I will review the following:

- Informed consent obtained for each participant
- Adherence to protocol eligibility criteria
- CRF completion
- Documentation of device use on the subject
- Monitor data and quality through routine review of submitted data to identify and follow-up on missing data, inconsistent data, or data outliers

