- Check and review of the regulatory binder and all essential documents
- Review of all SAEs and subject withdrawals
- Enrollment issues and targets
- Protocol amendments and their approval by the IRB
- Protocol deviations
- Personnel changes and required training
- Verifying continuous institutional review board (IRB) approval
- Any other issue as deemed important to the conduct of the study

Reporting and Follow-up:

If there are any significant findings, the S-I will follow-up any noncompliance, potential noncompliance, data irregularities, or other deficiencies identified along with a description of any actions taken, to be taken, or recommended, including the person responsible for completing actions and the anticipated date of completion.

4.0 Description of the Investigational Device:

Prototype Description:

The cryo-anesthesia device is a handheld instrument measuring approximately 10 inches in length and 1.5 inches in diameter, and weighing 0.8 pounds. A $4 \times 4 \text{ mm}^2$ area at the tip of the device is placed against the eye and cooled to a user-specified temperature setpoint between -5 and -10°C via activation of a switch on the device (**Figure 2**). The temperature setpoint is selected prior to device activation. Ocular surface cooling slows conduction of pain fibers in the conjunctiva (outermost layer of the eye) and the sclera (white of the eye) to a depth less than a millimeter. The key features of the device include a temperature regulating feedback loop that maintains highly accurate and precise temperature control and an integrated timer that controls the duration of cooling, both of which facilitate sufficient cooling and prohibit excessive cooling. Two small protrusions on the tip leave temporary indentations on the surface of the eye to guide placement of the intravitreal needle. The cooling region of the device is located on a replaceable metal tip. An “ON” switch is first activated to cool the contact region of the device, after which this region is placed against the eye, initiating rapid cooling to anesthetize the injection site while simultaneously marking the cooled location. After the specified cooling time is reached, the device is removed, immediately after which the physician performs intravitreal injection.

Figure 2 | Cryoanesthesia device.

Safety Features:

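### Section 3.1 has the data of withdrawing patients destroyed, so CA side effects that lead to withdrawal are lost to every later look of the only suspension rule

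*Protocol*

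**What the plan says.** **Suspension rule.** Section 2.3.3.2 plans interim analyses every 12 weeks or after every 10th treated patient, whichever is first. The sponsor "will suspend the study if there appears to be significantly more ocular side effects following CA". The scored signs are subconjunctival hemorrhage, hyperemia, conjunctival injection and keratopathy, within 30 minutes and at 1 day (section 2.4.1). No other provision in the protocol is tied to suspending the study.

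**Who leaves, and what happens to the data.**
- Section 3.1: a patient who cannot bear the cold tip for the full time and would "be unable to receive full CA, that patient would be removed from the study".
- Section 3.1: "If a patient withdraws from the study, the patient data will be destroyed". There is no exception for safety data.
- Section 3.1: "Another patient will be recruited to take their place", provided this fits the study time frame. Section 2.3.2.2 also plans replacement.
- Section 2.3.2.2: if a patient does not need, "or refuses, an injection in either eye, they will be removed from the study".

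**Oversight.** The interim monitoring in section 3.2, after 20 and after 40 enrolled, includes "Review of all SAEs and subject withdrawals". Its stated purpose includes checking that "Reported data are accurate, complete, and verifiable from source documents".

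**The concern.** A suspension rule on side effects needs the outcomes of the patients who fared worst. Section 3.1 sits under a heading about adverse effects and orders data destroyed for the group in which CA harm is most likely to be found. A SAP can choose the test and the analysis set, but it cannot restore destroyed data, so this is not a detail that can be left to it.

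The other routes do not fill the gap. IRB reporting in section 3.0 needs an effect that is device-associated, serious and unexpected, all three together. The scored signs are described as common after injection. The device risk named in section 1.3 is already expected: "The risks of the CA device include mild ocular discomfort secondary to the cold temperature". The sponsor-investigator's review in section 3.2 is not linked to suspension and, once the data are destroyed, can see at most that someone left.

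There is a second, smaller consequence. The pilot is meant to find the most effective temperature and time (section 1.3.1), with 10 patients per CA group. Replacement leaves non-completion at each setting out of that comparison unless it is reported separately.

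**Working it through.** **1. The plan's own figure.** 4 CA groups × 10 = 40 patients, as in section 2.2.2, which also expects all 40 to complete. The protocol states no test, level, sign rate or withdrawal rate for the rule, so there is nothing further to reproduce. Everything below rests on assumptions.

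**2. How little it takes.** Assume an exact two-sided McNemar test on discordant pairs at 0.05.
- 6 patients worse on CA, 0 worse on SOC: p = 2 × 0.5^6 = 0.031.
- 5 against 0: p = 2 × 0.5^5 = 0.063.

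Destroying one patient's data can reverse the result.

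**3. Direction.** Let p be the true rate of signs in CA eyes and w the share of patients with an affected CA eye who leave and are replaced. The rate among those who stay is p(1 − w)/(1 − pw). With p = 0.60:
- w = 0.10: 0.54/0.94 = 0.574
- w = 0.25: 0.45/0.85 = 0.529
- w = 0.50: 0.30/0.70 = 0.429

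With 40% on SOC, the visible excess shrinks from 20 points to about 17, 13 and 3. Expected patients lost before 40 stay: 40pw/(1 − pw) = 2.6, 7.1 and 17.1.

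**4. Chance of suspending by 40 patients.** Simulation: looks at 10, 20, 30 and 40 pairs, cumulative data, independent eyes, 60,000 runs, CA worse with p < 0.05.

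| Signs, CA vs SOC | w = 0 | 10% | 25% | 50% |
|---|---|---|---|---|
| 60 vs 40%, only affected CA eyes lead to leaving | 40% | 32% | 20% | 5% |
| 25 vs 5%, same | 65% | 57% | 42% | 18% |
| 60 vs 40%, affected SOC eyes lead to leaving equally often | 40% | 40% | 39% | 36% |
| 25 vs 5%, same | 65% | 60% | 51% | 30% |

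If nobody leaves, or leaving is unrelated to signs, there is no loss. With no true difference (20% or 40% in both eyes) and everyone kept, the rule triggers in 2 to 3% of trials.

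**5. What keeping the data recovers.** The w = 0 column treats every leaver as a complete pair. A patient who leaves after the CA eye and before the SOC eye has no pair. If half the leavers are of this kind (assumption), a pairs-only test in the 60 vs 40% case recovers to about 36%, 30% and 20%, not to 40%.

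**6. Cold-tip intolerance.** Suppose all intolerant patients are excluded, and signs occur in 30% of tolerant CA eyes and 20% of SOC eyes. If intolerant eyes also have 30%, the chance of suspending is about 15% with or without them. Only if they have 70% does a gap appear: 20%, 26% and 39% with all data, at 5%, 10% and 20% intolerance, against about 15% after exclusion.

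**7. Unreported non-completion.** Expected removals before n complete, at intolerance rate t, are nt/(1 − t). For n = 40 and t = 5%, 10%, 20%: 2.1, 4.4 and 10. For one group of 10 at t = 30%: 4.3.

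**The case against.** The case against has real substance.

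- **Population.** A reader might infer that the rule compares only patients who stay in, so that CA harm leading to withdrawal never reaches it. Section 2.3.3.2 restricts the comparison to no population and counts patients treated. Someone who withdraws after a look may have counted in that look. The loss is to later looks.
- **Removed is not withdrawn.** A reader might infer that the data of the intolerant patient, or of the one who refuses the other eye, are also destroyed. The destruction sentence is written for a patient who *withdraws*; the others are *removed*, and the protocol does not say what becomes of their data. Nor does it say that their 24-hour examination is dropped.
- **Intolerance is not a scored sign.** Keeping those data adds no event to the rule by itself. The loss in step 6 depends on the assumed 70% against 30%, which the protocol does not support.
- **Rates.** Section 2.3.2.2 calls refusal extremely rare, section 2.2.2 expects full completion, and some patients have both eyes treated at one visit. With equal leaving for either eye, the 60 vs 40% loss is only 40% to 36%.
- **Conflict with section 3.2.** The completeness requirement concerns reported data, and the number of withdrawals and their reasons could be reviewed without outcomes. This weakens the charge of contradiction. It still leaves that review with nothing on what happened in the eye.

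All of these limit the reach and size of the point. None removes the destruction sentence or its effect on later looks.

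**Conclusion.** The point holds in limited form. Followed as written, section 3.1 deletes the safety data of patients who withdraw, and so takes CA side effects that lead to withdrawal out of every later look of the only suspension rule. The bias is towards not suspending whenever withdrawal is more likely after CA harm. Its size cannot be derived from the protocol. The falls in step 4 are an upper-bound illustration under an assumed test, assumed sign rates and assumed leaving rates, and they should not be read as expected losses or as what the fix would regain.

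For removed patients the defect is silence: the protocol does not say whether their data are kept, and replacement leaves non-completion by CA setting out of the comparison meant to choose temperature and time.

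The change should be made because it is cheap and because destroyed data cannot be recovered later.

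**What to change.** 1. In section 3.1, replace the destruction sentence: data collected up to withdrawal or removal are kept, as far as consent allows.
2. In section 2.3.3.2, base the interim side-effect comparison on all eyes in which study anesthesia was started. Use a method that takes in patients with only one treated eye, for example per-eye proportions by anesthesia with an allowance for pairing, and not complete pairs alone.
3. At each look, report by CA group the number started, the number not completing CA or withdrawn, and the reason.
4. Reconcile sections 2.3.2.2, 2.3.3.2, 3.1 and 3.2, so that *removed* and *withdrawn* are distinguished and the data rule for each is stated.

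Replacement for the pain endpoint may continue. The suspension threshold and the handling of CA intolerance stay with the sponsor.

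Cost: an IRB amendment, possibly a consent amendment, and one more block in the interim table. Single-eye data add less information than a pair, so the comparison regains only part of what complete pairs would have given.

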Patients receiving SOC undergo the risk of increased corneal keratopathy. In addition, patients receiving the SOC have an increased risk of post injection pain. The risk of mild ocular discomfort

with CA is mitigated by the use of proparacaine and also poses less risk to patients than topical lidocaine.

1.3.1 Primary Objective:

We plan to carry out a pilot study to collect preliminary data on the effectiveness of the cryoanesthesia (CA) device in minimizing the pain caused by intravitreal injections (IVT) and determine the most effective temperature and time of treatment. Specifically, we intend to record patients' subjective injection pain. The study will be carried out in patients receiving bilateral injections, and one eye will be anesthetized using the CA device, with the fellow eye receiving anesthesia via a topical lidocaine gel (SOC), a common method of providing anesthesia in current clinical practice.

1.3.2 Exploratory Objective(s):

We will measure injection preparation pain, 4-hr, and 24-hr post injection pain. Patients will rate ocular irritation immediately after injection as well as 4 and 24 hours after injection (1 – no irritation; 2 – mild irritation 3 – moderate irritation 4- marked irritation). Patients will rate visual function in the treated eye immediately after injection as well as 4 and 24 hours after injection (1 – no changes from baseline; 2 – mild blurring of vision 3 – moderate blurring of vision 4- marked blurring of vision). Physicians will record patients' objective response to intraocular needle penetration (1 – no pain/movement; 2 – mild pain/movement 3 – marked pain/movement with the injection). In addition, physicians will record the following common ocular side effects following IVT: subconjunctival hemorrhage (SCH), conjunctival hyperemia, and conjunctival injection. These will be assessed via a slit lamp examination performed within 30 minutes and 24 hours of the administration of the intravitreal injection. In addition, each eye will be assessed for other signs of anterior segment toxicity, including AC reaction or hypotony. Patients will be examined or receive a call 1 week after the injection to assess any adverse effects.

1.4 Anticipated duration of the clinical investigation:

[figure not shown]

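### The side-effect score (exploratory endpoint 6) grades subconjunctival hemorrhage on two unlinked scales, and the recording lists in 1.3.2 and 2.3.3.2 do not match it on corneal keratopathy

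*Protocol*

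**What the plan says.** **The score.** Endpoint 6 in 2.4.1 is a three-level physician score covering four signs at two times: "within 30 minutes of administration of the intravitreal injection and 1 day following the injection (SCH, conjunctival hyperemia, conjunctival injection, and corneal keratopathy"). Level 1 means no side effects. The wording that separates level 2 (mild) from level 3 (marked) is "trace to 1+ SCH, conjunctival hyperemia, conjunctival injection, or corneal keratopathy; 3: Marked ocular side effects (SCH involving at least 25" percent of the ocular surface. For the other three signs, marked is "2-4+ conjunctival hyperemia or conjunctival injection, or 2-4+ corneal keratopathy". Item 4 of 2.4.2 repeats the same criteria.

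**The recording lists.** Section 1.3.2 lists "subconjunctival hemorrhage (SCH), conjunctival hyperemia, and conjunctival injection. These will be assessed via a slit lamp examination performed within 30 minutes and 24 hours". It names three signs, and keratopathy is not among them. Section 2.3.3.2 opens with the same three: "Physicians will record the following common ocular side effects following IVT: SCH, conjunctival hyperemia, and conjunctival injection". It ties them to the same slit-lamp examination at 30 minutes and 24 hours. It then says that at the 1-day examination "the physician will again record the presence of SCH, conjunctival hyperemia, conjunctival injection, and corneal keratopathy", which is four signs.

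**Why keratopathy matters here.** The risk discussion in section 1.3 names keratopathy among the primary risks of the study. It also says that patients receiving standard-of-care anesthesia (SOC) carry an increased risk of it.

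**The concern.** An ordinal score works only if every finding falls in exactly one category. Three of the four signs meet that requirement because they stay on one plus scale. SCH does not, because its lower category uses a plus-grade and its upper category uses an area. Two physicians who see the same hemorrhage could score it differently while both follow the protocol, and for some hemorrhages neither would find a category.

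The keratopathy mismatch is a different kind of problem. The endpoint needs a sign at 30 minutes that the procedural sections do not tell staff to record then. A sign not looked for at that examination cannot be recovered later. It is also a sign on which the protocol itself expects the cryoanesthesia (CA) and SOC eyes to differ.

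**Working it through.** No sample size, power or error rate is involved, and the plan states no figure to reproduce. The check is to apply the written rule to each possible finding and then compare the lists.

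**1. SCH under the rule as written.** Inputs from 2.4.1: mild is trace to 1+; marked is an area of at least 25%. The protocol does not define the SCH plus scale. I assume it runs to 4+, as it does for the other signs, and I treat plus-grade and area as separate observations because the text does not connect them.

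| SCH plus-grade | Area under 25% | Area 25% or more |
|---|---|---|
| Trace, 1+ | mild | mild and marked |
| 2+, 3+, 4+ | no grade | marked |

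So the SCH categories are neither exhaustive (lower left cell) nor mutually exclusive (upper right cell).

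**2. The other three signs.** Trace and 1+ are mild; 2+, 3+ and 4+ are marked. Each level has exactly one grade. The defect is confined to SCH.

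**3. Sensitivity: suppose the plus-grade is itself a measure of area.** Let *u* be the largest area still called 1+. The protocol gives no *u*, so I vary it.

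- *u* below 25%: a gap from *u* to 25% and no overlap. With *u* = 10%, hemorrhages above 10% and below 25% have no grade.
- *u* = 25%: only a tie at the boundary.
- *u* above 25%: an overlap from 25% to *u* and no gap. With *u* = 40%, areas from 25% to 40% meet both grades.

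Under this assumption at most one defect remains. Neither remains only if mild means all SCH under 25%, which the protocol does not say.

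**4. Keratopathy by section and time.** I take the 24-hour and 1-day examinations to be the same visit, since 2.3.3.1 has patients return at 24 hours for the anterior segment examination.

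| Section | 30 minutes | 24 hours / 1 day |
|---|---|---|
| 2.4.1 endpoint 6 and 2.4.2 item 4 | scored | scored |
| 1.3.2 | not listed | not listed |
| 2.3.3.2, first list | not listed | not listed |
| 2.3.3.2, 1-day examination | – | listed |

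The endpoint and 1.3.2 disagree at both times. The endpoint and 2.3.3.2 taken as a whole disagree at 30 minutes only. The wording of the 1-day sentence implies that keratopathy was already recorded once, but the list before it does not contain it.

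**The case against.** **The gap and overlap depend on how plus-grade is read.** This stands in part. If plus-grade measures area, only one of the two can be present, as step 3 shows. But the protocol does not define 1+ SCH, and the one definition that removes both defects is not written.

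**An unwritten rule that the highest grade wins would settle the overlap.** True, and many graders would apply it. It would not fill the gap: where SCH is the only sign, an SCH above 1+ and under 25% would still have no grade.

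**Endpoint 6 and 2.4.2 already require keratopathy at both times, so the shorter lists are loose wording.** This is fair. Data are lost only if staff follow 1.3.2 or 2.3.3.2 rather than the endpoint sections. The protocol does not say which governs, and 2.3.3.2 is the section that describes the safety procedures.

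**Could this be left to a statistical analysis plan?** A convention for the overlap could. A sign not recorded at the examination, or an area or grade never captured, could not be supplied afterwards.

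**Stronger readings the documents do not support.** A reader might infer that the score is also defective because it gives no grade to AC reaction or hypotony. It is not: the score is limited to four named signs, and the protocol sets these findings beside it ("In addition, each eye will be assessed for other signs of anterior segment toxicity, including AC reaction or hypotony"). Whether they enter the interim comparison is a detail that an analysis plan may hold. A reader might also infer that the flaw corrupts the safety rule, under which the investigators "will suspend the study if there appears to be significantly more ocular side effects following CA". That rule names no score. Endpoint 6 is the only physician side-effect score in the document, so a link is plausible, but it is an inference.

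**Conclusion.** Two wording defects hold, and both are minor.

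First, the SCH categories in endpoint 6 are neither exhaustive nor mutually exclusive as written, because mild and marked use different scales with no link. This rests on reading plus-grade and area as separate; if plus-grade is an area measure, one defect remains at most.

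Second, the lists in 1.3.2 and 2.3.3.2 do not match the endpoint on keratopathy: 1.3.2 at both times, and 2.3.3.2 at 30 minutes. Staff working from those sections would not capture a sign that the endpoint scores.

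The protocol gives no rates for SCH by grade and area or for early keratopathy, so the size in eyes or patients is unknown and none is claimed. The endpoint is exploratory in a pilot study. The primary injection-pain endpoint, the 1-day recording of keratopathy under 2.3.3.2, the 1-week call and the review of serious adverse events are unaffected. Confidence is high on the textual mismatches and low on any practical consequence.

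**What to change.** 1. In 2.4.1 endpoint 6 and 2.4.2 item 4, define mild and marked SCH on a single metric, either area or plus-grade, with adjoining cut-points that leave no gap and no overlap. If plus-grade is chosen, define the SCH grades.
2. In 1.3.2 and in the first list of 2.3.3.2, add corneal keratopathy so that both sections match endpoint 6 at 30 minutes and at 1 day. The reference in 2.3.3.2 to a repeat recording then becomes correct.
3. Carry both changes into the case report form.

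The cost is small: an edit to four sections and the form, and one more sign recorded at an examination already planned. No visits or patients are added.
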